3.3.2. Refinement of indications for surgical treatment of patients with SPCs

Patient clinical characteristics, symptoms and imaging data will be used in a model to predict symptom and QoL improvement following resection of SPCs.

4. PROJECT PLAN

We propose a single-centre, prospective controlled cohort study. Unlike previously published studies, which were retrospective cohort studies, this cohort will have a priori defined enrolment criteria, data points, outcomes and is powered to answer the study's questions. Given the patient numbers required (N=40) it is feasible to carry out the study in a single centre. The main advantages this design are maximum homogeneity of the study's variables and simplicity of its execution. However, if there is interest from other UK untints the study will be expanded under strict conditions of adherence to the study protocol and subject to governance approvals. This would accelerate recruitment.

As a result of Amendment 1, 21 consecutive patients who underwent an operation during the 5-year period prior to the commencement of the study (i.e. since 1st January 2016) and completed the required questionnaires and consented to participating in the study will be included in the total number of 40 surgically treated patients.

The primary outcome will be assessed once 40 surgically treated patients reach 12-months follow up. Since all the data required to assess the primary outcome was collected as a part of clinical care and will be available if patients consent for this to be used in the study, it may only be necessary to recruit 19 patients since the commencement of the study in order to achieve the primary objective as well as secondary objectives 3.2.1. and 3.2.2. of the study.

We will analyse and publish the result of the study with N=40. At that point, the cohort will consist of patients who underwent surgery before and after the commencement of the study. We will also evaluate the available data pertaining to the rest of the secondary of objectives (3.2.3, 3.2.4) and exploratory objectives (3.3.1 and 3.3.2). These data will be less complete and results less informative, but we believe this is a practically and ethically beneficial compromise to mitigate the negative impact of the COVID-19 pandemic.

4.1. INCLUSION CRITERIA

- Age =/> 16 years
- Pineal cyst > 9mm in maximum diameter (Májovský et al., 2017)
- Symptom category B (total score ≥5) according to Eide and Ringstad(Eide and Ringstad, 2017) Figure 1_Eide symptoms
- Willingness and ability to comply with study specific procedures and completion of QoL and symptoms questionnaires.
- Written informed consent

Acta	Neurochir	2017	159:349	-361

Symptom	Severity	Score
Headache	No	0
	Minor-moderate	1
	Severe	2
Nausea/vomiting	No	0
	Yes	1
Dizziness	No	0
	Yes	1
Visual disturbances	No	0
	Yes	1
Episodic loss of consciousness	No	0
	Yes	1
Lethargy/fatigue	None-moderate	0
	Severe	1
Cognitive impairment	No	0
	Minor-moderate	1
	Severe	2
Transient neurological deficits	No	0
	Yes	1
Total score		0/10 - 10/10

Symptom category A (none-moderate), 0–4/10 scores; symptom category B (much-severe), 5–10/10 scores

4.2. EXCLUSION CRITERIA

Evidence for alternative diagnoses/pathological processes causing presenting symptoms

4.3. RECRUITMENT STRATEGY AND SCREENING

When patient receive a diagnosis of a symptomatic pineal cyst (SPC) during a routine neurosurgical clinic consultation at the Addenbrooke's Hospital in Cambridge they will be informed about the possibility of taking part in this study by the patient clinical care team.

Patients referred to neurosurgical clinic for evaluation of their pineal cyst, either symptomatic or asymptomatic will be seen as per current practice. If a diagnosis of a symptomatic pineal cyst (SPC) is made (SPC > 9mm, Eide and Ringstad symptom B category), patients will be screened against inclusion and exclusion criteria (see Section 4.1 and 4.2). If fulfilling the entry criteria, patients will be offered participation in the study. Patients will be advised about the aims, expected benefits and risks of surgery as per current practice. Patients who request surgery will undergo an operation as per existing care pathway. Patients who chose not to undergo surgery will pursue conservative management as per existing care pathway. Interested patients regardless the pathway they have chosen will be explained the study and will be given a Participant Information Sheet (PIS). If they wish to join the study they will sign a Consent Form for participation in the study.

We anticipate that recruitment of the required number of patients treated by surgery will take approximately two years (N=40). The follow up for the primary outcome measure will take additional year. The study specific follow up assessments will be performed at one year after surgery for the primary efficacy outcome measure and SPC-related symptoms review. Given the relatively low burden posed by administering and filling in of the of the questionnaires, one early (3 months following surgery) and two late (at 2 and 3 years after surgery) surveys of symptom control and QoL will be performed (see also attached Flow Chart – Appendix 7 and Flow Table – Appendix 8).

Eligible participants who chose not to undergo surgery (this is an entirely clinical and not a research-related decision) will be recruited the non-surgery (conservative treatment) cohort (see also attached Flow Chart – Appendix 7 and Flow Table – Appendix 8). This is to

investigate/explore the QoL difference between surgery and non-surgery patients, both at diagnosis (baseline) and 3, 12, 24 and 36 months after treatment (one of the secondary objectives).

4. 4. NUMBERS AND METHODS OF ANALYSIS.

4.4.1. Primary outcome and sample size

The primary efficacy outcome measure is the change of role functioning scale of the EORTC QLQ c30 questionnaire at 12 months after surgery.

It is anticipated that a considerable clinical effect will be achieved, that is, an improvement of at least 20 points in a 0-100 scale in the role functioning scale. Using the estimated standard deviation of 42 at pre-surgery (retrospectively assessed) and 18 at 6 months post-surgery (prospectively assessed)(Fedorko, Zweckberger and Unterberg, 2018), with a conservative assumption of the correlation coefficient between pre- and post-surgery scores being 0.5, the estimated standard deviation of the difference between pre and post-surgery is 36. With a 5% significance level, 90% power, 37 participants are required to detect the 20 points using a paired t-test.

Allowing for some non-compliance and to maximise the yield from the secondary outcome measures we aim to recruit 40 participants. The assumptions used for sample size estimation will be monitored by the Study Steering Committee (see below). The conservatively treated patients, i.e. those who chose not to undergo surgery, will be recruited until the completion of surgically-treated patients. No power calculations are required as outcome measures related to the conservatively treated (non-surgery) cohort are among secondary objectives of this study.

4.4.2. Secondary outcomes

The secondary outcomes are:

- 1. Change in all in items of QoL as defined by the EORTC QLQ-C30 questionnaire before and at 3, 12, 24 and 36 months following resection of SPC
- 2. Change of individual symptoms before and at 3, 12, 24 and 36 months following resection of SPC
- 3. Change in the results neuropsychological tests at 12 months following surgery when compared to baseline (before surgery)
- 4. Difference in severity of symptoms and QoL at baseline between patients who chose surgical and non-surgical treatment
- 5. Assessment of symptoms and QoL over (at diagnosis and 3, 12, 24 and 36 months later) in patients who chose not to undergo surgery
- 6. Development of a model to identify anatomical (based in MRI scans) and clinical (symptoms) predictors of improvement of QoL after surgery for SPC

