	2. Assessment of symptoms at 1 year and also at 2 and 3 years after					
	surgery.					
	3. Assessment of all aspects of quality of life and symptoms in patients					
	who did not undergo surgery (= conservative management) at the time					
	of diagnosis and at 1, 2 and 3 years after joining the study; and					
	investigation the differences at baseline and follow up between those					
	treated surgically and conservatively.					
	4. Comparison of objective neuropsychological assessments before the					
	operation and at 1 year after surgery.					
	5. Development of a model to identify anatomical (based in MRI scans)					
	and clinical (symptoms) predictors of improvement of QoL after surgery					
	for SPC					
Study design	Prospective observational cohort study					

Date and Version No: 28/06/2021 Version 1.2

Interventions No interventions. This is an observational study.	
---	--

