3.2.3. Quality of life and symptoms of patients treated conservatively

We will assess Quality of Life and Symptoms of patient who chose conservative management at enrolment and at 3, 12, 24 and 36 months following the diagnosis of SPC. These data will also serve to compare baseline Quality of Life and Symptoms between patients managed surgically and conservatively. We will explore the differences of outcomes of patients who

choose conservative and surgical treatments with adjusting confounding factors. This cohort will also give us an idea about changes in severity of symptoms and QoL over time.

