3.2.4. Cognitive status and emotional wellbeing – before and after surgery

As with most other resective brain surgery, SPC patients undergo detailed objective neuropsychological assessments before and after surgery. For the sake of the study this will be done systematically, with a standard protocol and in predefined intervals, i.e. before and 12 months after surgery. (Appendices 1-3)

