4.4.4. Statistical analyses

The paired t-test will be applied to the primary efficacy analysis for all patients received surgery treatment. A detailed statistical analysis plan will be drafted prior to any analyses performed.

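### Neuropsychological change is measured in operated patients only, so 12-month change cannot be separated from retest gain, and the bias runs towards missing a decline

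*Supplement*

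**What the plan says.** Section 4.4.2 of protocol version 1.2 lists as secondary outcome 3: "Change in the results neuropsychological tests at 12 months following surgery when compared to baseline (before surgery)". Section 3.2.4, headed cognitive status and emotional wellbeing, describes objective assessments around surgery and says "this will be done systematically, with a standard protocol and in predefined intervals, i.e. before and 12 months after surgery". The synopsis gives the same two-point comparison for operated patients: "Comparison of objective neuropsychological assessments before the" operation and at one year.

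For the conservative cohort, section 3.2.3 says "We will assess Quality of Life and Symptoms of patient who chose conservative management at enrolment and at 3, 12, 24 and 36 months". Section 4.3 gives that cohort's purpose as to "investigate/explore the QoL difference between surgery and non-surgery patients", and item 5 of section 4.4.2 again lists only symptoms and quality of life. No neuropsychological test is named for these patients.

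On analysis, section 4.4.4 says "The paired t-test will be applied to the primary efficacy analysis for all patients received surgery treatment", and then "A detailed statistical analysis plan will be drafted prior to any analyses performed". No statistical analysis plan is shown. Section 4 (the Amendment 1 text) concedes that data for objective 3.2.4 will be less complete.

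**The concern.** People often score better on a performance test the second time because they have met it before. A two-point comparison in treated patients alone attributes that gain to the treatment, or lets it cancel a loss. The usual remedies are an untreated group tested at the same interval, a correction from published retest norms, or alternate test forms. The shown text has no tested comparator and names neither of the other two.

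The direction is what matters. Section 2 makes the safety of surgery one of the reasons for the study, and these are its only objective measures of cognition. A retest gain can turn a real loss into an apparent absence of change, or a small loss into an apparent gain. Results read that way would inform patients choosing surgery and the planning of the randomised trial for which this study is meant to be a pilot.

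**Working it through.** **The plan's own figure.** The protocol gives no number for the neuropsychological outcome. Its one calculation (section 4.4.1) is for role functioning, and it reproduces. SD of the difference = √(42² + 18² − 2 × 0.5 × 42 × 18) = 36.5, stated as 36. A paired t-test at two-sided 5% with a 20-point effect and n = 37 has power 0.90 to 0.91. It says nothing about cognition.

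**Structure of the problem.** Let T be the true mean change and g the mean retest gain, both in baseline SDs. The study observes T + g in operated patients. With no untreated group tested and no external value for g, T is not identified.

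**Inputs for an illustration.** From the documents:
- 40 operated patients.
- As few as 19 of them recruited after the study starts (synopsis and section 4).

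Assumed, because the documents give nothing:
- True decline T = −0.3 SD.
- g from 0 to 0.3 SD.
- Retest correlation r from 0.6 to 0.8.
- A paired t-test on mean change, used only to show the mechanism.

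SD of change = √(2(1 − r)) = 0.894, 0.775 and 0.632 for r = 0.6, 0.7 and 0.8.

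| Assumed g | Expected mean change | Chance of a significant decline, N = 40 | N = 19 |
|---|---|---|---|
| 0 | −0.3 SD | 0.54 to 0.83 | 0.28 to 0.50 |
| 0.1 | −0.2 SD | 0.28 to 0.50 | 0.15 to 0.26 |
| 0.2 | −0.1 SD | 0.10 to 0.16 | 0.07 to 0.10 |
| 0.3 | 0 | 0.025 | 0.025 |

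Both values of N are optimistic or uncertain. Only patients tested before and 12 months after surgery contribute, and the protocol does not say how many of the earlier-operated patients were.

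**What individual scoring can recover.** Flag a patient whose change falls more than 1.645 × SD of change below the expected retest gain. The threshold is 1.47, 1.27 and 1.04 SD for r = 0.6, 0.7 and 0.8.
- For a true loss of 1.5 SD, sensitivity is 0.51 to 0.77 with the gain removed. It is 0.38 to 0.60 if a gain of 0.3 SD is ignored.
- For a true loss of 1.0 SD at r = 0.8, sensitivity is about 0.47. If 5 of 40 lose 1.0 SD, about 0.47 × 5 = 2.4 are flagged, beside 0.05 × 35 = 1.75 false flags per test.
- Chance flags accumulate. An unharmed patient has a 1 − 0.95⁵ = 23% chance of at least one flag over five independent tests, and 1 − 0.95¹⁰ = 40% over ten. The number of tests is assumed; correlated tests would give less.
- If no patient declines, the one-sided 95% upper bound on the rate is 1 − 0.05^(1/40) = 7.2% for 40 paired patients and 1 − 0.05^(1/19) = 14.6% for 19.

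**The case against.** **The analysis is deferred.** Section 4.4.4 leaves everything but the primary test to a later plan, and practice correction is commonly specified there. This stands in part. A later plan could adopt norm-based scoring, but it cannot supply tests that conservative patients never took. Who is tested, and when, is already settled in the protocol.

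**A group mean will hide harmed patients.** A reader might infer this from outcome 3, but the documents do not support it. The paired t-test is named for the primary outcome only, and no summary measure is stated for the tests. An illustration built on it is also fragile. With g = 0.3, r = 0.8 and 5 of 40 losing 1.0 SD, the mean is 0.3 − 0.125 = +0.175 SD. The SD of change is √(0.4 + 0.125 × 0.875) = 0.71 and the standard error 0.71/√40 = 0.113, so t is about 1.55 (p about 0.13). That is not a significant improvement.

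**This outcome is the test of cognitive harm.** A reader might infer this too. The objective is headed cognitive status and emotional wellbeing, and no safety conclusion is tied to it. Other information exists: patient ratings of memory, speaking and concentration at 3 and 12 months, QLQ-C30 items 20 and 25, and complication monitoring. The ratings and items are self-report, and the monitoring names no cognitive measure, so none replaces an objective test.

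**Alternate forms may be in use.** Section 3.2.4 refers to appendices for the assessments, and no neuropsychological appendix is shown. This stands: it cannot be said that identical forms are repeated. Alternate forms would reduce retest gain but need not remove it.

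**The protocol is candid.** It says results for 3.2.4 will be less informative and that a randomised trial is likely to be needed. That acknowledges incompleteness, not a directional bias.

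**Conclusion.** The concern holds as a limit on what outcome 3 can show. Neuropsychological change is planned in operated patients only, while the conservative cohort, followed over the same period, is not scheduled for these tests. Observed change therefore combines true change with retest gain, and the bias runs towards missing a decline. The structure follows from the documents; the size does not. The table rests wholly on assumed values of g, r and T, and shows that a gain of 0.2 to 0.3 SD would be enough to mask a true decline of 0.3 SD in most repetitions. The documents do not establish that a group mean will be used, that this outcome is the formal test of harm, or that the same forms are repeated. For a secondary outcome with a cheap remedy, this should be corrected before analysis; it does not touch the primary objective.

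**What to change.** Extend the definition of secondary outcome 3, in section 4.4.2 or in the analysis plan before any data are examined:

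- Beside the average change, score each patient's change against published retest norms, where these exist for a comparable interval (practice-corrected reliable change). State whether alternate forms are used.
- Per test, report the number with paired assessments, and the number and proportion with reliable decline and with reliable gain, with exact confidence intervals.
- State the number of flags expected by chance across the battery, so that isolated flags are not over-read.
- Where no suitable norms exist, report change uncorrected. State that improvement or absence of decline cannot be separated from practice, and is not evidence of cognitive safety or benefit.

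The cost is wording and some scoring work on data already planned, with no extra testing. There are downsides. Norms may be missing for some tests or for a 12-month interval, individual flags have limited sensitivity, and reported gains may look smaller. Testing the conservative cohort at the same interval would give a direct comparator, but at more burden and with patients who differ by their choice of treatment, so it is not needed for this correction.

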4.4.3. Exploratory outcomes

- development of a model to identify anatomical (MRI) and clinical (symptoms) predictors of improvement of QoL after surgery for SPC

4.4.4. Statistical analyses

The paired t-test will be applied to the primary efficacy analysis for all patients received surgery treatment. A detailed statistical analysis plan will be drafted prior to any analyses performed.

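### The primary paired t-test is set for all operated patients but uses only those with a 12-month score; the resulting bias can go either way, and a repeated-measures model would use the scheduled 3-month data

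*Supplement*

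**What the plan says.** The primary endpoint is defined in section 4.4.1: "The primary efficacy outcome measure is the change of role functioning scale of the EORTC QLQ c30 questionnaire at 12 months after surgery". Section 4.4.4 fixes the method and the population together: "The paired t-test will be applied to the primary efficacy analysis for all patients received surgery treatment". Its next sentence promises a detailed analysis plan before any analysis; that plan is not among the documents.

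Section 4.4.1 finds that 37 patients are needed and sets recruitment at 40, with the reason "Allowing for some non-compliance" and a wish for more secondary data. Section 4.5.2 lets patients leave at any time without giving a reason. Role functioning will also be measured between baseline and 12 months, because section 4.4.2 lists "Change in all in items of QoL as defined by the EORTC QLQ-C30 questionnaire before and at 3, 12, 24 and 36 months".

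Under Amendment 1 (section 4), 21 of the 40 are patients operated on before the study began, who enter if they completed the required questionnaires and consent. That section says all primary-outcome data were collected in clinical care. Section 5 is looser: it describes these patients as holding part or all of the questionnaire set, with later forms still to come.

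**The concern.** Method and population agree only if every operated patient returns a 12-month form. Once one is missing, the test as named runs on completers, and the protocol does not say whether the test or the population gives way.

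The three extra patients protect power but not the estimate. The primary result is one mean change with no randomised comparison, so if the patients lost differ in their change from those who stay, the difference passes straight into the headline figure. Two scheduled measurements carry information about a patient with no 12-month score, the baseline and the 3-month score, and the paired t-test uses neither for that patient.

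**Working it through.** **1. The plan's own figure.** Section 4.4.1 gives "an improvement of at least 20 points in a 0-100 scale in the role functioning scale", an "estimated standard deviation of 42 at pre-surgery (retrospectively assessed) and 18 at 6 months post-surgery", and a "correlation coefficient between pre- and post-surgery scores being 0.5".

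SD of the difference = √(42² + 18² − 2 × 0.5 × 42 × 18) = √(1764 + 324 − 756) = √1332 = 36.5; the plan uses 36. The exact two-sided 5% paired t-test at 90% power gives N = 37 with either value, so the stated figure reproduces. With SD 36, power is 92.9% at 40 and 90.8% at 37. Losing three patients (3/40 = 7.5%) does not harm power.

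**2. Effect of losing three on the mean.** If the true mean change is 20 and the three lost average x, the remaining 37 average (40 × 20 − 3x)/37:

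| Mean change x of the three lost | Completer mean | Bias |
|---|---|---|
| +20 (no different) | 20.0 | 0 |
| +10 | 20.8 | +0.8 |
| 0 | 21.6 | +1.6 |
| −16 (1 SD below the mean) | 22.9 | +2.9 |

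The standard error at N = 40 is 36/√40 = 5.7.

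**3. Who might be lost.** Simulation with normal scores, SD 42 before and 18 after surgery, pre/post correlation 0.5, true change 20, N = 40, and 3 of the 19 new patients lost. Assumptions not in the documents: 3-month SD 18, baseline-to-3-month correlation 0.5, 3-to-12-month correlation 0.5 to 0.85. The alternative estimator is the likelihood one for this pattern: regress the 12-month score on baseline and 3-month scores in completers, average the prediction over all 40, and subtract the mean baseline.

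| Which 3 of the 19 are lost | Bias, completer paired difference | Bias, likelihood model |
|---|---|---|
| At random | about 0 (SE about 6.05) | about 0 (SE about 5.87) |
| At random from the lower half of 3-month improvement | about +2 | about 0.2 or less |
| Least 3-month improvement | about +4 | about 0.2 or less |
| Low absolute 3-month scores | −0.7 to −1.3 | about 0.2 or less |
| Smallest 12-month change (unseen) | about +4.3 | under +1 |
| Lowest absolute 12-month scores (unseen) | −0.3 to −0.5 | +0.5 to +1.4 |

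**4. Why the sign turns.** With these inputs, a patient one point lower at 3 months is expected to be 0.5 × 42/18 = 1.17 points lower at baseline, but only 0.5 to 0.85 points lower at 12 months. The expected 12-month change is therefore larger by 1.17 − 0.85 = 0.32 to 1.17 − 0.5 = 0.67 points. Losing patients with low absolute 3-month scores removes larger-than-average gains and pulls the completer mean down. Losing patients with poor improvement removes smaller-than-average gains and pushes it up.

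**The case against.** The strongest reply is that section 4.4.4 defers detail to an analysis plan that is not shown, and missing-data rules usually sit there. On that view, the reference to all operated patients merely separates them from the conservative cohort, and a paired t-test could be run on multiply imputed data. Part of this stands. Silence on missing data would not by itself be a fault, and a reader should not infer that the final analysis is known to drop patients uncorrected. But the protocol has already fixed a test and a population, and a later plan that follows both inherits the mismatch.

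Second, the size rests on assumed loss. This stands. A reader might infer that the estimate will be inflated, but the documents give no rate, direction or pattern, and step 4 shows the bias can be negative. The moderate upward case, about +2, is one third of a standard error. Normal scores with SD 42 also fit a 0–100 scale poorly: centred at 50, the limits lie 50/42 = 1.19 SD away and about 23% of values fall outside, so the extreme rows are the least reliable.

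Third, near-zero bias for the model is built in when loss depends on 3-month data that the model conditions on. This also stands. A reader might infer that 3-month data already in hand can repair the estimate. The forms are scheduled, not secured; section 5 leaves open how complete they are for the earlier patients, and a patient absent at 12 months may have missed 3 months too. When loss follows unseen 12-month values some bias remains, and in the last row of the table the model does worse than the t-test.

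Fourth, it is tempting to say that all 12-month loss must fall on the 19 new patients. Section 4 points that way and section 5 does not fully agree, so the simulation treats it as an assumption.

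**Conclusion.** The point holds in a limited form. The stated test cannot cover the stated population once a 12-month score is missing, the plan expects some losses, and the completer estimate can then be biased in either direction. With 3 of 19 new patients lost, the bias is about +2 to +4 points if loss follows poor 3-month improvement and about −1 point if it follows low absolute 3-month scores, against a standard error of about 6 and a target change of 20. These figures rest on the plan's SDs and correlation, normality, and the assumed 3-month SD and correlations.

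A likelihood model is the better primary analysis because it uses more of the scheduled data and removes nearly all bias when loss depends on observed scores. It does not help in every case. Nor can any model fitted within the 40 correct the selection of the 21 earlier patients, for whom completed questionnaires are a condition of entry. The change is worth making before 12-month data are examined; the issue does not by itself overturn the study.

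**What to change.** In section 4.4.4, and then in the analysis plan:

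- Make the primary analysis a likelihood-based repeated-measures model of role functioning at baseline, 3 and 12 months, with time as a factor and unstructured covariance. Include all operated patients with a baseline score and use 3-month scores where available.
- Report the 12-month-minus-baseline contrast with its 95% confidence interval as the primary result.
- Keep the completer paired t-test as a sensitivity analysis.
- Add a missing-not-at-random analysis that shifts the predicted 12-month scores of those lost by a stated range in both directions. With 3 of 40 missing, a shift of δ moves the estimate by 3δ/40; for example, −20 points moves it by −1.5.
- Report how many operated patients lack a 12-month score, separately for the 21 earlier and 19 new patients, and state that selection of the former is not corrected.

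The cost is a few sentences and slightly more analysis work, with no new data. With no losses the estimate is unchanged; with random losses it is slightly more precise (standard error about 5.87 against 6.05). The price is the assumption that data are missing at random given baseline and 3-month scores.
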